 - If patient still produces sputum - negative *P. aeruginosa* culture from sputum, blood or pleural fluid

Secondary Clinical Efficacy Endpoints

1. Proportion of patients with Clinical Cure at Day 28
2. Proportion of patients with Clinical Cure at Day 14
3. All-cause mortality
4. Pneumonia-related mortality
5. Proportion of patients with Clinical Cure at Day 7
6. Change from baseline in respiratory functional assessment: Time on mechanical ventilation (including if tracheostomy is in place). Time on supplemental oxygenation. Measures of

respiratory health such as changes in PaO₂/FiO₂, using arterial blood gases and/or pulse oximetry measurements.

7. Mean change from baseline in overall clinical status measured by SOFA scores.
8. Health economics: antibiotic utilization, duration of stay in the ICU, duration of hospitalization, duration of intubation with ventilation or duration of mechanical ventilation if tracheostomy is in place.

Microbiological Endpoints

Microbiological outcome of the index *P. aeruginosa* pneumonia based on the data provided by the local microbiology laboratory and central microbiology laboratory.

Eradication of *P. aeruginosa* at Day 21 and 28. Eradication is considered as obtained when a specimen of respiratory secretions is obtained between the visit day and Day 28 and is negative. When no specimen is obtained within this time frame, microbiological outcome will be assessed as “Eradicated” only if the study subject is not receiving any antibiotic active against the initial strain after the study drug administration visit day and displays no signs and symptoms of pneumonia.

Change in bacterial load related to the index *P. aeruginosa* on the basis of quantitative or semi-quantitative cultures by the local microbiological laboratory.

Pharmacokinetic Endpoints

Assessment of the PK parameters during full PK sub-study.

Assessment of the PK parameters during sparse PK sub-study.

Safety Endpoints:

1. Assessment of clinical adverse events
2. Assessment of clinical laboratory safety tests
3. Assessment of immunogenicity to Aerucin®

STATISTICAL ANALYSES:

Continuous data will be summarized by means, standard deviations, median, min, and max. Categorical data will be summarized by frequency and percentages.

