6 STUDY PROCEDURES

An overview of the study is provided below (**Figure 6-1**). Day-by-day details are provided in (**Table 6-1**). In summary, any patient with VAP, who is intubated, older than 18 years (at least 20 years of age in Taiwan and at least 19 years of age in South Korea) and who signed an informed consent, will enter a screening phase dedicated to identifying any pathogen that is present, and in particular, verifying whether *P. aeruginosa* is present. This screening phase is critical to ensuring that no potentially eligible patient is missed. Therefore, the related activities should be organized and managed proactively. Participation of key hospital staff is very important, including personnel involved in managing infectious diseases in the institution, the local microbiology department, and any relevant personnel.

If a culture from a valid airway specimen (BAL, mini-BAL or ETA) obtained within 72 hours of randomization is positive for *P. aeruginosa*, the subject can be randomized on this sole basis provided that all eligibility criteria are met, and that a new valid airway specimen is obtained prior to treatment. This baseline airway specimen will be sent to the site's local microbiology laboratory for quantitative/semi-quantitative culture. These baseline culture results are not required prior to randomization.

The sites will obtain airway specimens for culture prior to treatment (baseline), as medically indicated, at time of extubation, and at Day 28 (if not extubated prior to Day 28). Airway specimen cultures will be sent to the local microbiology laboratory for culture, including identification of genus and species, quantification and susceptibility testing as outlined in the microbiology laboratory manual.

Isolates of unique organisms from airway specimen cultures will be sent to the central lab. The central microbiology laboratory will confirm identification and perform standardized antibiotic quantitative/semi-quantitative culture, susceptibility testing and serotyping on target pathogens as outlined in the microbiology laboratory manual.

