
 1. To be performed if medically necessary. Follow-up airway specimens to be obtained as medically necessary and prior to extubation and at Day 28 (if not extubated prior to then) for quantitative or semi-quantitative culture. 2. SOFA and respiratory data to be collected on Day 0, 12 hours after treatment initiation and on Day 4, 7, 14, 21, 28 while intubated and mechanically ventilated. Parameters for SOFA score calculation should not be older than 72 hours. 3. ADA only at screening / baseline and Day 28, or at early termination. 4. Pre-dose PK sample to be obtained prior to treatment initiation. 5. PK samples to be obtained for the FULL PK sub-study at the following times after initiation of treatment: 2 hours (end of infusion), 4h, 12h, and 24 hours and 1 sample at each of the following visits: Day 4, 7, 14, 21, and 28. 6. PK samples for the SPARSE PK sub-study at the following times after initiation of treatment: 1 sample at 2 hours (end of infusion), 1 sample at either 4h, 12h, or 24 hours post-treatment initiation (inclusive) and 1 sample at any of the following visits: Day 4, 7, 14, 21, or 28. 7. Eligible subjects are randomized on Day -1, Treatment day is Day 0 for the purpose of monitoring and collecting the required samples over the first 24 hours. 8. Clinical Cure will be assessed at Day 7, 14, 21, 28 for the analytical purposes. 9. Discharge data to be obtained when discharge occurs or Day 28, whichever occurs first. 10. Patients with pneumonia who are intubated are eligible for screening regardless of the type of pneumonia, which will be recorded at the time of screening for all study subjects. 11. Vital signs will be recorded at baseline prior to treatment (time 0) and then at 1, 2, 4, 12, and 24 hours post treatment. Vital signs will also be recorded daily thereafter. 12. In addition to the screening timepoint, chest x-ray(s) are to be taken at any time as medically indicated. 13. Women of child bearing potential must take a urine or serum pregnancy test at the time of Screening. 14. For subjects with early discharge, effort must be made to perform all protocol defined procedures outlined for End of Study/Early Termination. 15. Subjects who decide to discontinue study assessments prior to Day 28 will receive a study exit safety follow-up phone call on key days (Day 4, 7, 14, 21, 28) until Day 28 (+7 days) to assess Clinical Cure, survival and the status of any adverse events. 16. Changes in PaO₂/FiO₂ ratio (e.g. by arterial blood gases), if available and whenever possible OR changes in non-invasive measures of oxygenation (e.g. by pulse oximetry) 17. A few days before or after the specified date is acceptable (± 2 days) 					

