6.6 Day 4, 7, 14, and 21: Required full assessments

- All daily assessments as detailed above are required whether the subject is in the ICU or has been transferred out of the ICU.
- Perform full assessment of the clinical status of pneumonia
- Document Clinical Cure, persistence or re-infection/new infection of index pneumonia using the daily assessments described above.
- Microbiology:
 - **Airway specimens are to be obtained:**
 - **At any time when as medically indicated**
 - **At the least, a valid airway specimen (BAL, mini-BAL or ETA) is to be obtained just prior to extubation. Ideally, an ETA specimen would be preferred for the airway culture. If BAL or mini-BAL, make sure that either BUN or urea is collected at or about the same time of sampling.**
 - **An aliquot (i.e. half of this specimen) is to be reserved for assessing bioavailability (refer to microbiology lab manual for instructions).**
 - **If not obtained on Day 4, 7, 14, and 21, the nearest specimen collected will be used to assess microbiological outcome.**
 - Obtain airway specimens for local and central laboratory assessment (by BAL, mini-BAL, or protected endotracheal tube aspiration) for standard microbial culture (quantitative, semi-quantitative). Other sampling methods, including sputum, are acceptable after extubation.
 - Obtain isolates for assessment by the central laboratory.
 - Record microbiological assessments from the local laboratory in the EDC system, including:
 - Assessment of the quality of the sample
 - Organism identification (genus and species)
 - Quantification
 - Any organisms identified,
 - The corresponding antibiotic susceptibility profile for each pathogen as determined by the local microbiology laboratory

- An assessment of microbiological outcome
- Physical exam
- Vital signs
- Adverse Events
- Concomitant Medications
- Respiratory health:
 - Mechanical ventilation parameters
 - PaO₂/FiO₂ ratio (e.g. by arterial blood gases), if available and whenever possible OR changes in non-invasive measures of oxygenation (e.g. by pulse oximetry)
 - Use of supplemental oxygen
- Laboratory tests.
 - Standard safety tests (required on these days regardless of medical need)

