6.7 End of study (Day 28) or Early Termination

- Perform full assessment of the status of pneumonia
- Document final clinical outcome of the index pneumonia
- Airway specimens are to be obtained:
 - **At any time when as medically indicated**
 - **At the least, a valid airway specimen (BAL, mini-BAL or ETA) is to be obtained just prior to extubation. Ideally, an ETA specimen would be preferred for the airway culture. If BAL or mini-BAL, make sure that either BUN or urea is collected at or about the same time as sampling.**
 - **An aliquot (i.e. half of the specimen) is to be reserved for assessing bioavailability (refer to microbiology lab manual for instructions).**
 - **If not obtained on Day 28, the nearest specimen collected will be used to assess microbiological outcome.**
- Obtain airway specimens for local and central laboratory assessment (by BAL, mini-BAL, or protected endotracheal tube aspiration) for standard microbial culture (quantitative, semi-quantitative). Other sampling methods, including sputum, are acceptable after extubation.

- Obtain isolates for assessment by the central laboratory.
- Record microbiological assessments from the local laboratory in the EDC system, including:
 - Assessment of the quality of the sample
 - Organism identification (genus and species)
 - Quantification
 - Any organisms identified
 - The corresponding antibiotic susceptibility profile for each pathogen as determined by the local microbiology laboratory
 - An assessment of microbiological outcome
- Respiratory health:
 - Mechanical ventilation parameters
 - PaO₂/FiO₂ ratio (e.g. by arterial blood gases), if available and whenever possible OR changes in non-invasive measures of oxygenation (e.g. by pulse oximetry)
 - Use of supplemental oxygen
- Physical exam
- Vital signs
- Chest X-Rays at any time when as medically indicated
- All-cause mortality
- Adverse Events
- Concomitant Medications
- Laboratory tests
 - Standard safety tests (required on these days regardless of medical need)
 - For subjects participating in the **FULL PK** sub-study, PK sample is to be obtained on Day 28. For subjects participating in the **SPARSE PK** sub-study, a PK sample is to be obtained on Day 28 if it has not been collected previously at any of the following visits: Day 4, 7, 14, or 21.
 - ADA sample
 - Future biomarker sample, where applicable.
- Ensure that outcomes of all recorded adverse events are known, final and recorded.

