7.3 Microbiological Endpoints

1. Microbiological outcome of the index *P. aeruginosa* pneumonia based on the data provided by the local microbiology laboratory and central microbiology laboratory.
2. Eradication of *P. aeruginosa* at Day 21 and 28. Eradication is considered as obtained when a specimen of respiratory secretions is obtained between the visit day and Day 28 and is negative. When no specimen is obtained within this time frame, microbiological outcome will be assessed as “Eradicated” only if the study subject is not receiving any antibiotic active against the initial strain after the study drug administration visit day and displays no signs and symptoms of pneumonia.
3. Change in bacterial load related to the index *P. aeruginosa* on the basis of quantitative or semi-quantitative cultures by the local microbiological laboratory.

An antibiotic susceptibility profile will be obtained locally in order to confirm the effectiveness of the concomitant antibiotic regimen prior to enrollment and thereafter, as medically indicated.

Quantitative and semi-quantitative cultures will be performed locally prior to treatment (baseline), as medically indicated, just prior to extubation, and at Day 28 (if not extubated prior to Day 28).

Organism identification and antibiotic susceptibility profiles will be confirmed by the central microbiology laboratory for the purpose of confirming the infecting pathogen(s), and the adequacy of the concomitant antibiotic regimen.

Serotyping will be performed by the central microbiology laboratory.

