### 6.4.3. Microbiological Endpoints

Microbiological endpoints include the following:

- Eradication of index *P. aeruginosa* at Day 21 and 28;
- Re-infection/new infection defined as a reoccurrence of pneumonia due to *P. aeruginosa* within the 28-day follow-up period; and
- Change in bacterial load related to the index *P. aeruginosa* on the basis of quantitative or semi-quantitative cultures by the local microbiological laboratory.

Microbiological endpoints of eradication and re-infection/new infection will be determined based on quantitative/semi quantitative cultures performed by the local laboratory and testing of isolates performed by a central microbiology laboratory.

For microbiological outcome of eradication of index *P. aeruginosa*, if no specimen of respiratory secretions is obtained at the specific time point, the nearest microbiological data available prior to that day (Day 7, 14, 21, or 28) will be used, i.e. using LOCF approach. When there is no specimen obtained prior to that day, microbiological outcome will be assessed as “Eradicated” only if the study subject is not receiving any antibiotic active against the initial strain after the study drug administration and prior to that day and displays no signs and symptoms of pneumonia.

The eradication rate of index *P. aeruginosa* and reinfection rate of pneumonia due to *P. aeruginosa* will be summarized by treatment group based on the micro-ITT Population and analyzed using a stratified CMH test based on the stratification factors at randomization. The P-value from the stratified CMH test will be presented.

Change in bacterial load ( $\log_{10}\text{cfu/mL}$ ) related to the index *P. aeruginosa* based on the local microbiological laboratory will be presented by treatment group for the micro-ITT Population.

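### Day 21 and Day 28 eradication: the sampling passages conflict, and the two classification rules can place the same early-extubated subject on opposite sides

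*Protocol*

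**What the plan says.** **Definition.** The Synopsis, Protocol 7.3 and SAP 5.3 share one rule: "Eradication is considered as obtained when a specimen of respiratory secretions is obtained between the visit day and Day 28 and is negative". Without such a specimen, a subject counts as eradicated "only if the study subject is not receiving any antibiotic active against the initial strain after the study drug administration visit day" and has no signs or symptoms of pneumonia.

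**Sampling, restrictive passages.** Table 6-1 footnote 1, repeated under SAP Table 1, reads "Follow-up airway specimens to be obtained as medically necessary and prior to extubation and at Day 28 (if not extubated prior to then". Protocol Section 6 agrees: "The sites will obtain airway specimens for culture prior to treatment (baseline), as medically indicated, at time of extubation, and at Day 28", the last again only if not yet extubated. Protocol 7.3, which holds the definition, lists cultures at baseline, as medically indicated, and "just prior to extubation, and at Day 28 (if not extubated prior to Day 28".

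**Sampling, broader passages.** Protocol 6.6 (Day 4, 7, 14 and 21) and 6.7 (Day 28) each carry a bullet beginning "Obtain airway specimens for local and central laboratory assessment", with no condition on intubation. Both add: "Other sampling methods, including sputum, are acceptable after extubation".

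**Missing specimens.** SAP 6.4.3 differs from SAP 5.3: "if no specimen of respiratory secretions is obtained at the specific time point, the nearest microbiological data available prior to that day" is used (LOCF), and the presumption applies only when there is no prior specimen at all. Protocol 9.3.5 also looks backward. Protocol 6.5 to 6.7 use the nearest specimen without giving a direction.

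**Analysis.** SAP 6.4.3 tests the eradication rate in the micro-ITT population with a stratified CMH test and reports a p-value. Eradication is not among the ranked endpoints in SAP 6.4.2.

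**The concern.** The endpoint is tied to specimens from a late window, but the passages that set the sampling schedule do not secure one for a subject who comes off the ventilator early. Whether window data exist then depends on extubation, which happens after randomization and may differ between arms.

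The documents also give two answers for a subject without a window specimen. One looks back to the last culture, which for many would be the one taken at extubation. The other makes the subject a failure if active antibiotics were given after study drug. The choice between them could move the eradication rate substantially, and the arm with more early extubations would be affected more.

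At stake is how to read a stated microbiological objective (Protocol 2.5) and part of hypothesis 3 (Protocol 1.4). The primary endpoint and the ranked secondary endpoints are not affected.

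**Working it through.** **1. Plan figure.** No rate, power or sample size is stated for eradication, so there is no figure to reproduce. The inputs used from the plan are the assumed cure rates (65% placebo, 85% active) and 154 subjects (77 per group; 69 / 0.9 = 76.7, rounded up). Both are in Protocol 9.2 and SAP 4.

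**2. Fixed specimens against the windows, restrictive passages only.**

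| Subject | Fixed follow-up specimen | In Day 21 window (Day 21 to 28) | In Day 28 window (Day 28) |
|---|---|---|---|
| Extubated before Day 21 | Before extubation | No | No |
| Extubated from Day 21, before Day 28 | Before extubation | Yes | No |
| Still intubated at Day 28 | Day 28 | Yes | Yes |

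**3. The same subject under each rule.** Take a subject extubated on Day 6 with a negative culture just before, treated with an active antibiotic after Day 0, with no later specimen and no symptoms.
- Protocol 7.3 and SAP 5.3, read literally: there is no window specimen and the antibiotic condition fails, so not eradicated.
- SAP 6.4.3: the Day 6 culture is carried forward, so eradicated at Day 21 and Day 28.

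The rules also differ for a subject still intubated at Day 28. That culture lies in the Day 21 window under 7.3, but SAP 6.4.3 looks back from Day 21 and could use an older one.

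**4. How many subjects.** Extubation rates are not given. With the assumed cure rates as a rough proxy for extubation before Day 21:
- 0.65 × 154 = 100.1
- 0.85 × 154 = 130.9

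So about 100 to 131 of 154 would have no fixed specimen in the window.

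**5. How far the rules diverge.** All inputs in this step are assumptions:
- e = share extubated alive before Day 21.
- v = share still intubated, all with a window specimen.
- Deaths 1 − e − v = 15% to 25%, counted as not eradicated.
- s = share of early-extubated subjects who give a window specimen.
- Culture-negative rates (q_e, q_v) for extubated and intubated subjects: (0.70, 0.70) or (0.80, 0.40).
- No subject meets the presumption rule.

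Formulas:
- Literal 7.3 / SAP 5.3 rate = e·s·q_e + v·q_v
- SAP 6.4.3 rate = e·q_e + v·q_v
- Gap = e·(1 − s)·q_e
- Carried-forward share of successes under SAP 6.4.3 = gap / SAP 6.4.3 rate

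Example: e = 0.50, v = 0.35, s = 0, both q = 0.70. Literal: 0.35 × 0.70 = 0.245. SAP 6.4.3: 0.350 + 0.245 = 0.595. Gap: 0.350. Share: 0.350 / 0.595 = 59%.

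Ranges with s = 0:

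| e | Literal rate | SAP 6.4.3 rate | Carried-forward share |
|---|---|---|---|
| 30% | 18.0–38.5% | 42.0–59.5% | 35–57% |
| 50% | 10.0–24.5% | 50.0–59.5% | 59–80% |
| 65% | 4.0–14.0% | 52.5–60.0% | 76–93% |

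With s = 50% the gap halves. At e = 50% it falls from 35–40 points to 17.5–20 points, and the carried-forward share does not exceed 50% in any case examined (e up to 75%).

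**The case against.** **The visit sections do ask for specimens.** Sections 6.6 and 6.7 list airway specimens without an intubation condition and accept sputum, and their wording on specimens not obtained on the visit days presupposes collection then. This stands: a reader might infer that the protocol schedules nothing after extubation, but it contradicts itself rather than being silent. The broader reading is not secure either. Section 6.5 carries a similar bullet under daily follow-up, where it would mean daily airway sampling. All three sections name the pre-extubation specimen as the minimum. Section 8.8 lets cured, discharged subjects be followed by telephone, which yields no specimen.

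**Presumed successes.** A reader might infer that many successes would be presumed. The documents do not support that. Study drug is given on top of standard antibiotics, so few subjects should meet the condition of no active antibiotic after study drug, and SAP 6.4.3 presumes only when no prior specimen exists.

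**Size.** A reader might infer that most of the tested rate is carried forward, or that at most 15% of active and 35% of placebo subjects could have window data. Neither follows. The assumed rates concern investigator-assessed cure, for which extubation is not a stated condition. The adjudicated criteria exempt subjects expected to stay ventilated beyond Day 28. Those criteria also list a negative sputum culture among the parameters to consider, so cultures after extubation are contemplated.

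**Importance.** Eradication is outside the testing hierarchy. This stands and limits the severity.

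**Conclusion.** The point holds as two inconsistencies. The sampling passages disagree on whether an extubated subject is cultured at Day 21 and Day 28. SAP 5.3 and 6.4.3 can then classify the same subject in opposite ways. If the restrictive passages govern, whether window data exist depends on a post-randomization outcome.

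The size is conditional. The figure of about 100 to 131 of 154 rests on cure standing in for early extubation and on no sputum being cultured; it is neither a bound nor a forecast. The gap between the two rules, e·(1 − s)·q_e, is 21 to 24 points at 30% early extubation and 45.5 to 52 points at 65%, with no post-extubation specimens, and half that if half of those subjects give one. These inputs are assumed. Severity is modest: no ranked conclusion changes, but a reported p-value on a stated objective would be hard to interpret.

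**What to change.** 1. Reconcile Table 6-1 footnote 1 (and the SAP copy), Protocol Section 6 and 7.3 with 6.6 and 6.7, so that it is clear that an extubated subject who produces sputum at the Day 21 or Day 28 visit has it cultured.
2. Before unblinding, write one classification rule in both SAP 5.3 and 6.4.3: use any specimen from the visit day to Day 28 first, and only then carry an older one forward. State whether the pre-treatment specimen may be carried forward and when the presumption applies.
3. Report Day 21 and Day 28 eradication by arm, split into documented in the window, carried forward and presumed, with the documented-only result beside the CMH test.

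The cost is a schedule clarification, a few sputum cultures of a type already accepted, SAP wording and one table. The documented-only result remains a selected subset and should be read as descriptive. Testing the pre-extubation culture instead would avoid extra sampling, but it changes the stated Day 21 and Day 28 endpoint and is not needed to resolve the conflict.
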